Orange et al (2012) reviewed the clinical efficacy of SCIG and identified 13 clinical studies in a total of 482 patients representing more than 27,500 infusions. The rate of serious bacterial infections (SBIs) was the most common primary efficacy endpoint in these studies. Secondary endpoints included overall infections (ie, infections not meeting SBI criteria), missed days at work or school, days in hospital and days on antibiotics. Definitions of overall infections and SBI were not standardized across studies. In 6 studies, SBIs were defined by FDA criteria and included bacterial pneumonia, meningitis, sepsis, osteomyelitis or visceral abscess. In 2 studies, an SBI was defined as an infection requiring hospitalization.[3]

The rate of SBI was reported in 11 studies and varied from 0 to 0.09 events per patient per year. Infections were reported in 11 studies and varied from 2 to 5.18 events per patient per year. These rates are overall at least as low as those reported for IVIG studies.

To provide adequate protection from infection, a serum IgG concentration of >5 g/L following IgG therapy has been recommended. Several retrospective studies and one prospective study, however, have shown that higher serum IgG concentrations resulting from higher doses of IVIG are associated with a decreased incidence of infections.[3]

A previous meta-analysis in 16 individual studies of IVIG focused on the diagnosis of pneumonia, the most comparable endpoint, and demonstrated a statistically significant inverse correlation between higher IgG dose and a lower incidence of pneumonia, with a 27% decrease in incidence of pneumonia for every 100 mg/kg increase in dose.[13]

Despite its well-established safety profile, IVIG often leads to undesired symptoms ranging from mild systemic adverse reactions (including flushing, fever, muscle aches, tiredness, headache, and dizziness) to severe reactions (including chest pain, tachycardia, changes in blood pressure, aseptic meningitis, thrombosis, and renal failure).[4]

The slower rate of rise towards the peak serum IgG level and the truncation of its height are believed to be responsible for the much lower incidence of systemic adverse events (AEs) with SCIG. This is consistent with observations that many AEs of IVIG infusions are rate-related and have been repeatedly confirmed.[12]

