9.2.2 Efficacy Analysis Plan

The rate of SBI per person-year (bacterial pneumonia, bacteremia/sepsis, osteomyelitis/septic arthritis, visceral abscess, bacterial meningitis) during the CUTAQUIG treatment period will be presented as point estimates of the rate along with a 99% CI. Calculation of this confidence interval will account for intra-patient correlation in incidents following a compound Poisson process model. Furthermore, all observed SBIs will be listed individually and in full detail.

The duration of infection will be summarized by standard descriptive statistics by type of infection and by severity. The individual characteristics of each infection, including the time to resolution will be listed.

The use of antibiotics will be reported as a detailed list of all such medications, and the number of patients treated with antibiotics, the number of treatment episodes and the number of treatment days will be tabulated.

The US FDA Guidance for Industry on Safety, Efficacy, and Pharmacokinetic Studies to Support Marketing of Immune Globulin Intravenous (Human) as Replacement Therapy for Primary Humoral Immunodeficiency suggests that, based on historical data, a statistical demonstration of a serious bacterial infection rate per person-year less than 1.0 is adequate to provide substantial evidence of efficacy.^[25] Therefore, this background information will be used for a descriptive evaluation of the serious bacterial infection rate in this study as described above. Exploratory statistical testing may be performed if considered appropriate.

The QoL data will be presented descriptively by visit, along with the change from Baseline, defined as the Treatment Period Baseline Visit.

For Cohort 3, the change in total IgG trough levels when switching from weekly to every other week infusions will be tested confirmatory by means of a one-sided, paired t-test at the $\alpha=0.025$ level of significance. The following pair of hypotheses will be tested:

$$H_a: T_{eow} > T_w - 1 \quad \text{vs.} \quad H_0: T_{eow} \leq T_w - 1$$

where T_{eow} is the mean total IgG trough on steady-state dosing every other week, T_w is the same for weekly dosing, and a maximum decrease of 1 g/L for the mean total IgG trough level is considered acceptable.

T_w will be determined after completion of the Stabilization Period, T_{eow} at the final study visit.

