7.4. Derived and Computed Variables

The following derived and computed variables have been initially identified as important for the analysis of the primary and secondary target variables. It is expected that additional variables will be required. The SAP will not be amended for additional variables that are not related to the primary target or key secondary target variables. Any additional derived or computed variables will be 090-SAP-SCGAM-06-clean version3.0_13FEB2022

identified and documented in the SAS programs that create the analysis files. If the SAP is not amended, further derivations related to primary and secondary target variables will be described in the CSR.

- **Age** will be derived according to the usual definition that a person is n years old until she or he has completed her or his $(n+1)^{\text{th}}$ year of life, using the date of informed consent as the reference date. This is also the definition that will be applied for evaluation of the age related inclusion criteria [Unit: years]
- **Body Mass Index:** $\text{BMI} = (\text{Body weight}) / \text{Height}^2$ [Unit: kg/m^2]
- The **CUTAQUIG stabilization period** is defined for patients that did not participate in the SCGAM-03 trial as the period between the day of first treatment with study drug to the end of the observation period. This will usually be the treatment period baseline visit.
- The **CUTAQUIG treatment period** is defined as the period between the day of first treatment with study drug in a modified dosing regimen to the end of the observation period. For patients that previously completed the SCGAM-03 trial, this is also the period of first treatment with the SCGAM-06 study drug. The end of the observation period will usually be the termination visit.
- The **rate of serious bacterial infections** per year during regularly repeated treatment with CUTAQUIG will be calculated as $r = (\text{Total number of serious bacterial infections occurring in the stabilization and treatment periods}) / (\text{Sum of stabilization and treatment periods})$ [Unit: 1/years]
- The **rate of other infections** will be derived using the same method

Calculation of the confidence intervals of these rates will account for intra-patient correlation in incidents following a compound Poisson process model.[1]

With C_i infections for the i^{th} patient, and C total infections, the adjusted 2-sided 98% CI is calculated by:

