$$\left[e^{\ln(r) - 2.33 \cdot \sqrt{\frac{\sum C_i^2}{C^2}}} ; e^{\ln(r) + 2.33 \cdot \sqrt{\frac{\sum C_i^2}{C^2}}} \right]$$

If there are 0 infections, an alternative method will be used to approximate the upper bound on the 98% confidence interval using a chi-square distribution and the following SAS code:

```
data poisson;
events=0;
sumyrs=xxx;
ul=cinv(0.99,2*(events+1))/2;
rate=events/sumyrs;
ulinc=ul/sumyrs;
run;
where
sumyrs = duration of treatment in years
events = total number of events
```

rate = total number of events per person-year

ulinc = two-sided 98% CI - upper limit

- The **rate of infusions with one or more temporally associated AEs** will be calculated for each patient as $r = (\text{Number of infusions with one or more temporally associated AEs}) / (\text{Number of infusions started})$. An AE is defined as a temporally associated if, and only if, the onset (or worsening) is either during an infusion of study medication or within 72 hours of the end of the infusion. [Unit: N/A]

Property of Octapharma. Do not copy or distribute without written permission.

8. Study Subjects and Demographics

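### The SAP's confidence interval for the serious bacterial infection rate is inaccurate at 1 to 3 events, though no study-level conclusion turns on it; its level and exposure period also need reconciling with the protocol

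*SAP*

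**What the plan says.** SAP 7.4 defines the SBI rate as SBIs divided by the "Sum of stabilization and treatment periods". For one or more events, "the adjusted 2-sided 98% CI is calculated by" multiplying and dividing the rate r by exp(2.33 × √(ΣCᵢ²/C²)), where Cᵢ is patient i's count and C the total. Only at zero does the method change: "If there are 0 infections, an alternative method will be used", namely a chi-square limit coded as "ul=cinv(0.99,2*(events+1))/2". No rule covers small non-zero counts. SAP section 9 repeats the two-sided 98% level for SBIs, and SAP section 7 plans summaries overall and, where applicable, by cohort.

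Protocol 9.2.2 says that the SBI rate "during the CUTAQUIG treatment period will be presented as point estimates of the rate along with a 99% CI". It also wants the interval to allow for within-patient correlation. It cites an SBI rate below 1.0 per person-year from regulatory guidance, uses that figure for descriptive evaluation only, and leaves room for exploratory testing. Protocol 1.1 reports that the SBI rate in earlier subcutaneous immunoglobulin studies "varied from 0 to 0.09 events per patient per year".

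**The concern.** The formula relies on the log of the rate being roughly normal, which does not hold for one, two or three events. Those are the counts to expect here if the result is not zero. The planned method is therefore exact at zero and at its worst at one event, so the reported limit jumps between the two partly because the method changes. An interval labelled 98% would not have 1% in each tail, and a reader could misjudge a cohort's upper limit against 1.0.

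Separately, the two documents give different confidence levels and describe the exposure period differently. The reported interval therefore depends on which document is followed.

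**Working it through.** **Inputs.** Cohorts of at least 15, 15 and 35, about 65 in all (protocol 9.1, SAP 5); about 28 weeks on treatment per patient (SAP 4.1); background rate 0 to 0.09 per year (protocol 1.1). Dropout for this rate is not stated; zero loss is assumed, with 10% and 20% loss of person-time also tried. Person-years (PY) = patients × weeks × 7/365.25.

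- 15 patients, 28 weeks: 15 × 28 × 7/365.25 = 8.05 PY
- 35 patients: 18.78 PY
- 65 patients: 34.88 PY

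**The plan's own figures reproduce.** The two-sided 98% normal multiplier is 2.326, stated as 2.33. The zero-event code gives χ²(0.99; 2)/2 = 4.605 events, the exact Poisson limit.

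**Expected counts.** 0.09 × 34.88 = 3.1, so about 0 to 3 SBIs overall. In a 15-patient cohort at the top of that range, the mean is 0.09 × 8.05 = 0.724, and the chance of exactly one SBI is 0.724 × e^(−0.724) ≈ 35%.

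**Limits as event counts, each event in a different patient.** Then ΣCᵢ²/C² = 1/C, so the SAP limits are C × exp(±2.33/√C). The exact limits are χ²(0.01; 2C)/2 and χ²(0.99; 2C+2)/2.

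| Events | SAP lower | Exact lower | SAP upper | Exact upper | Upper, excess |
|---|---|---|---|---|---|
| 0 | – | – | 4.61 | 4.61 | none |
| 1 | 0.097 | 0.010 | 10.28 | 6.64 | 55% |
| 2 | 0.385 | 0.149 | 10.39 | 8.41 | 24% |
| 3 | 0.781 | 0.436 | 11.52 | 10.05 | 15% |
| 10 | 4.79 | 4.13 | 20.89 | 20.14 | 4% |

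The SAP upper limit barely moves between one and two events. Each tail should hold 1%. At one event, the Poisson probability of 1 or more at a mean of 0.097 is 1 − e^(−0.097) = 9.3%, and of 1 or fewer at a mean of 10.28 is e^(−10.28) × 11.28 = 0.04%.

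**As rates per year, 28 weeks, upper limit.**

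| Group | SBIs | SAP | Exact |
|---|---|---|---|
| 15 patients | 0 | 0.57 | 0.57 |
| 15 patients | 1 | 1.28 | 0.82 |
| 15 patients | 2 | 1.291 | 1.044 |
| 15 patients | 3 | 1.431 | 1.248 |
| 35 patients | 1 | 0.547 | 0.353 |
| 65 patients | 1 | 0.295 | 0.190 |
| 65 patients | 3 | 0.330 | 0.288 |

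With one SBI, the two methods fall on opposite sides of 1.0 only between 6.64 and 10.28 PY. Fifteen patients lie in that band at 24 weeks (6.90 PY; 1.490 against 0.962) and at 29 weeks (8.34 PY; 1.233 against 0.796). They stay in it with 10% loss at 29 weeks (1.370 against 0.885). With 20% loss at 28 weeks both limits exceed 1.0 (1.596 and 1.031). With 20 patients at 28 weeks (10.73 PY) both are below it: 10.28/10.73 = 0.96 and 6.64/10.73 = 0.62.

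**Repeat events.** Two SBIs in one patient give a SAP upper limit of 2 × exp(2.33) = 20.56 events, against 8.41 from the exact method, which ignores clustering.

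**Level.** At zero events in 34.88 PY, a two-sided 99% interval has upper limit −ln(0.005)/34.88 = 5.298/34.88 = 0.152; two-sided 98% gives 4.605/34.88 = 0.132.

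**The case against.** The strongest reply is that nothing decisive depends on this interval. SBI is a secondary endpoint, and protocol 9.2 treats additional intervals as exploratory. The 1.0 figure is used descriptively for the study, with no per-cohort criterion. The upper limit errs against the product and so cannot produce a false claim that the rate is below 1.0; the lower limit plays no part in that comparison. All of this stands. It rules out what a reader might infer from the cohort example, that the formula would overturn the trial's SBI conclusion. The documents set no such decision, and the split needs exactly one SBI and 6.64 to 10.28 PY.

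Zero events is also very plausible. Protocol 1.1 reports no SBIs in 61 patients and 3,497 weekly infusions of this product, about 3,497 × 7/365.25 = 67 PY if each infusion covers a week. At zero the SAP is already exact. That lowers the chance that the problem appears but does not remove it.

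The exact limits assume independent events, while protocol 9.2.2 asks for an allowance for within-patient correlation. This is a fair limit on calling them the correct answer. But with one event ΣCᵢ²/C² equals 1 whatever the correlation, so the 55% excess is not a correlation adjustment. With repeat events the point does matter, and the fix has to respect it.

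On the document differences, the protocol gives no sidedness for its 99%. If a one-sided bound was meant, its upper limit equals that of a two-sided 98% interval. The protocol's wording on the period could also cover all time on the product. A reader might infer two outright contradictions; the text supports only two ambiguities that need settling.

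**Conclusion.** The concern holds as a point about accuracy. From one to three SBIs, the planned interval is shifted upward at both ends: the upper limit by 55%, 24% and 15%, and the lower limit from 0.010 to 0.097 events at one event. These sizes assume each event is in a different patient and events are Poisson.

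No formal or study-level conclusion changes. Cohort 3 and the whole study stay well below 1.0 under either method at one SBI, and in a 15-patient cohort over 28 weeks both methods exceed 1.0 at two or three. The one visible effect is a 15-patient cohort with a single SBI, shown as 1.28 instead of 0.82 on the assumption of 28 weeks without loss. The correction is worth making because it is nearly free and the interval would otherwise not have the coverage on its label. The level and period wording is a separate, smaller matter of reconciliation.

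**What to change.** In SAP 7.4 and 9:

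- For the SBI rate at every count, make the exact Poisson limits the main descriptive interval. The upper limit is the SAP's own "ul=cinv(0.99,2*(events+1))/2" with the actual event count in place of the fixed zero; the lower limit is `cinv(0.01,2*events)/2`, set to 0 when there are no events. Divide both by person-years.
- Whenever any patient has more than one SBI, report the compound-Poisson interval beside it as a sensitivity result. The main method then does not depend on the data, and clustering remains visible.
- Keep the compound-Poisson formula for all infections, where counts are larger and repeats are common.
- State one confidence level with its sidedness and one exposure period for the SBI rate, and record these and the change of method as departures from protocol 9.2.2.

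The cost is a few sentences and a small edit to existing SAS code, with no new data. The downside is that the exact limits assume independent events, which is why the second interval is shown. If the SAP can no longer be amended, the exact limits can be added to the study report and labelled as unplanned, as SAP section 2 provides.

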8.1. Disposition of Subjects and Withdrawals

All patients enrolled in the study will be accounted for. Descriptive summaries of population data will be provided overall and by study cohort; these will include

- The frequency and percent of patients in each analysis population, age strata (pediatric and adult) and enrollment group
- The disposition of patients (including number of patients enrolled, number of patients treated, number of completers)
- study withdrawals by reason of withdrawal

8.2. Protocol Violations

Protocol violations will be checked on complete data for all patients prior to defining the analysis populations.

The final decision regarding inclusion/exclusion of patients from the analysis sets will be taken based on protocol adherence reports during data review meetings before database lock, data release and final analysis applying the definitions in section 6.

Major protocol violations as well as all violations leading to exclusion from the PP population will be summarized by type of violation. Individual patients with these protocol violations will be listed.

8.3. Demographics and Other Baseline Characteristics

Descriptive summaries of the demographic and other baseline characteristics will be completed for the populations specified below, overall and by study cohort as applicable; these include:

- Demographics (Age, Gender, Race/Ethnicity, Height, Weight, BMI (calculated), ABO blood type, primary immunodeficiency disease type)
(SAF, FAS, PP)
- Medical History (SAF)

Medical history will be coded with the Medical Dictionary for Regulatory Activities (MedDRA, according to the version specified in the Data Management Plan). Incidences of findings in medical history will be summarized by MedDRA system organ class (SOC) and preferred term (PT)

- Prior and Concomitant Medications (SAF)

Prior medications will be presented by non-SCIG product and SCIG product. Concomitant medications will be presented by pre-medication and non-pre-medication. A medication will be considered a pre-medication if it is given prior to an infusion to prevent one or more previously experienced infusion-related symptoms.

Medications will be coded using the WHO Drug Dictionary (according to the version specified in the Data Management Plan). Incidences of prior and concomitant medications will be summarized by ATC level 2 and ATC level 4

- Baseline Physical Examination, including vital signs (SAF) at Screening, Stabilization Period Baseline (Week 0), and Treatment Period Baseline

8.4. Measurement of Treatment Compliance

The following parameters will be listed and summarized per patient and/or per infusion:

- Body weight
- Actual dose (total and per kg body weight, based on the latest available weight measurement)
- Total dose of CUTAQUIG administered
- Total number of infusions administered
- Total volume of solution administered
- Infusion times
- Overall amount of product administered (only included in data listings)
- Maximal volume administered (in total and per kg body weight)
- Injection sites
- Injection flow rates

Deviations from the planned treatment schedule will be examined by summarizing the number of patients with infusions, and the number of infusions, that deviate from the scheduled intervals by more than 2 days, and by listing all cases with more than two days deviation individually. The number of patients with infusions, and the number of infusions with an incorrect dose administered will also be summarized.

Study drug exposure will be summarized by planned volume (mL), volume infused (mL), CUTAQUIG dose administered (mg), and CUTAQUIG dose administered by baseline body weight (mg/kg).

9. Efficacy Analysis

The rate of SBI per person-year (bacterial pneumonia, bacteremia/sepsis, osteomyelitis/septic arthritis, visceral abscess, bacterial meningitis) during treatment with CUTAQUIG will be summarized descriptively and a two-sided 98% CI will be presented. Calculation of this CI will account for intra-patient correlation in incidents following a compound Poisson process model. This analysis will also include summaries of the number of patients with any SBI, the number of SBIs, and the duration of treatment (annualized). Furthermore, all observed SBIs will be listed individually and in full detail.

Infections will be analyzed in the same manner as SBIs, except the analysis will be presented by Stabilization Group and Treatment Group separately. Further, the duration of infection will be summarized by severity. The individual characteristics of each infection, including the time to resolution will be listed.

The use of antibiotics will be summarized descriptively and reported as a detailed list of all such medications, and the number of patients treated with antibiotics, the number of treatment episodes and the number of treatment days will be tabulated. Similarly, systemic antibiotic usage will be presented where antibiotics with the following routes will be excluded: SC, SUBL, OCUL, OTIC, RECT, TOP, BUC, NASAL, TDERM, TOP OD, TOP OS, or TOP OU.

The QoL SF-10 and SF-36 data will be presented descriptively by summarizing derived component scores from PRO CoRE 2.1 Smart Measurement® System software. Observed and change from baseline (defined as the Treatment Period Baseline Visit) data will be summarized by visit for the following derived component scores:

SF-10- Physical Summary Score and Psychosocial Summary Score;

SF-36- Physical Functioning 0-100 and Norm-based Score, Role Physical 0-100 and Norm-based Score, Bodily Pain 0-100 and Norm-based Score, General Health 0-100 and Norm-based Score, Vitality 0-100 and Norm-based Score, Social Functioning 0-100 and Norm-based Score, Role Emotional 0-100 and Norm-based Score, Mental Heath 0-100 and Norm-based Score, Physical Component Score, and Mental Component Score.

The derived scores and the responses from the SF-10 and SF-36 survey questions will be presented in the listings.

Total serum IgG trough levels will be summarized for observed and change from baseline during the Treatment Period for Cohort 1, 2, and 3.

For Cohort 3, the change in total IgG trough levels when switching from weekly to every other week infusions will be tested confirmatory by means of a one-sided, paired t-test at the $\alpha=0.025$ level of significance. The following pair of hypotheses will be tested:

$$H_a: T_{eow} > T_w - 1 \quad \text{vs.} \quad H_0: T_{eow} \leq T_w - 1$$

where T_{eow} is the mean total IgG trough on steady-state dosing every other week, T_w is the same for weekly dosing, and a maximum decrease of 1 g/L for the mean total IgG trough level is considered acceptable.

T_w will be determined after completion of the Stabilization Period, T_{eow} at a given subject's final study visit where an IgG trough level is collected and reported within a suitable visit window. If a subject terminates from the study prior to the end of study visit (2 weeks following Week 24 infusion), then the last study visit where a valid IgG trough level was collected will be considered T_{eow} .

10. Safety and Tolerability Analyses

The safety analysis will comprise descriptive statistics, tabulations and listings of all TEAEs, safety laboratory results, vital signs and physical examination findings.

